11.4.4 Analyses of Patient Reported Outcomes

Self-reported patient satisfaction and hypoglycemia: Satisfaction scores at 6 and 12 months will be compared between treatment groups using a MMRM approach as described for the continuous efficacy variables. To adjust for the baseline differences between treatment groups, logistic regression will be conducted, adjusting for randomization strata of HbA1c target, SU use ever (y/n), GLP-1 RA use ever (y/n) and baseline A1c (as continuous).

Global Effectiveness Scale (GES): At each study endpoint, the proportion of patients and providers who reported “Excellent” or “Good” at 6 and 12 months will be analyzed using CMH tests adjusting for randomization strata.

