2.1.7.1 Diabetes Treatment Satisfaction Questionnaire Status Version

The DTSQs is a validated questionnaire to assess patient satisfaction with treatment and patient perception of BG control (3). The DTSQs will be used to evaluate patient satisfaction with treatment and patient perception of BG control over a several week period. The DTSQs is comprised of 8 questions which are answered on a Likert scale from 0 to 6. Responses to these questions would be summarized into the three domain scores of Total Treatment Satisfaction (Questions 1, 4-8), Hyperglycemia Perception (Question 2) and Hypoglycemia Perception (Questions 3) such that a higher score would be indicative of better satisfaction. Mean differences in scores between groups would be evaluated to understand the impact of treatment on patient satisfaction. DTSQs will be evaluated at Screening, Day 1, 6 months and 12 months in this study.

The total treatment satisfaction score and the 2 other scores are determined by computing the mean of item responses:

- Total treatment satisfaction score: sum of Items 1, 4, 5, 6, 7 and 8, ranging from 0 (no satisfaction) to 36 (high satisfaction),
- Perceived frequency of hyperglycemia score: Item 2, ranging from 0 (none of the time) to 6 (most of time),
- Perceived frequency of hypoglycemia score: Item 3, ranging from 0 (none of the time) to 6 (most of time).

The DTSQs endpoints are:

- Average scores on total treatment satisfaction from DTSQs at 6 months and 12 months,
- Average scores on hyperglycemia perception from DTSQs at 6 months and 12 months; and,
- Average scores on hypoglycemia perception from DTSQs at 6 months and 12 months.

Additionally, on these 3 scores (total treatment satisfaction, hyperglycemia perception and hypoglycemia perception), evaluation will be performed on:

- Change from baseline to 6 months,
- Change from baseline to 12 months,
- Change between 6 and 12 months.

Additional endpoints are:

- Percentage of patient responders on total treatment satisfaction score, defined as patients presenting a change from baseline to respectively Month 6 and Month 12 of at least the distribution-based minimal clinically important difference (MCID) value ([Section 2.5.1](#)).
- Percentage of patient responders on perceived frequency of hyperglycemia score, defined as patients presenting a change from baseline to respectively Month 6 and Month 12 of at least the standard MCID value ([Section 2.5.1](#)).

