- Percentage of patient responders on perceived frequency of hypoglycemia score, presenting a change from baseline to respectively Month 6 and Month 12 of at least the standard MCID ([Section 2.5.1](#)).

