2.1.7.2 Diabetes Treatment Satisfaction Questionnaire Change Version

The DTSQc was developed from the original DTSQ to evaluate the change in treatment satisfaction at a specific time point (4).

The DTSQc will be used to produce a measure of relative change in satisfaction rather than measure of absolute satisfaction, which is subject to ceiling and floor effects.

A score for DTSQc treatment satisfaction items (Questions 1, 4-8) range from -3 to +3, and the sum of the treatment satisfaction scores range from -18 to +18.

Positive scores are indicative of increases in treatment satisfaction relative to one year ago (start of the study).

Perceived hyperglycemia (Question 2) and hypoglycemia (Question 3) items have scores that range from -3 to +3 in the DTSQc, with higher scores indicating more frequent perceived hyperglycemia or hypoglycemia by the end of the study.

To control for baseline scores, DTSQs will be used as a measure of treatment satisfaction at baseline. DTSQc will be evaluated at 12 months in this study.

The total treatment satisfaction score and the 2 other scores are determined by computing the mean of item responses:

- Total treatment satisfaction score: sum of Items 1, 4, 5, 6, 7 and 8, ranging from -18 (deterioration in treatment satisfaction) to +18 (improvement in treatment satisfaction),
- Perceived frequency of hyperglycemia score: Item 2, ranging from -3 (fewer problems than before with hyperglycemia) to +3 (more problems),
- Perceived frequency of hypoglycemia score : Item 3, ranging from -3 (fewer problems than before with hypoglycemia) to +3 (more problems).

The DTSQc endpoints are:

- Average scores on change in total treatment satisfaction from DTSQc at 12 months,
- Average scores on change in hyperglycemia perception from DTSQc at 12 months,
- Average scores on change in hypoglycemia perception from DTSQc at 12 months.

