2.4.7 Analyses of patient reported outcome variables

The patient report outcomes (PRO) analyses will be performed on the ITT population.

Self-reported treatment satisfaction

DTSQs and DTSQc scores at 6 and 12 months will be compared between treatment groups using an ANCOVA approach as described for the continuous efficacy variables. The ANCOVA model with satisfaction score as the dependent variable includes HbA1c target and other stratification factors used at randomization: SU use (y/n), GLP-1 RA use (y/n) and baseline HbA1c (as continuous) in the model.

The consistency between results of DTSQs change from baseline to 12 months and DTSQc scores at 12 months will be assessed.

Cumulative distribution function of score changes from baseline at 6 and 12-months will be plotted by treatment arm for each of the 3 DTSQs scores. Cumulative distribution function of 12-month DTSQc scores will be plotted by treatment arm.

Hypoglycemia Patient Questionnaire

Items of the Hypoglycemia Patient Questionnaire will be summarized by descriptive statistics. a graphical presentation will also be provided.

The proportion of patients reporting one or more episodes of either moderate or severe hypoglycemia will be compared between treatment groups using the same logistic regression model as for GES detailed in following paragraph.

Global Effectiveness Scale

At each study endpoint, the proportion of patients and providers who reported “complete control of diabetes” or “marked improvement of diabetes” at 6 and 12 months will be analyzed using a logistic regression same as the primary efficacy analysis. The dependent variable is the “complete control/marked improvement” (y/n). The logistic model includes HbA1c target and other stratification factors used at randomization: SU use (y/n), GLP-1 RA use (y/n) and baseline HbA1c (as continuous) in the model.

Additionally, at each time point (6 months and 12 months), all response choices for both patients and provider will be summarized by descriptive statistics.

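### The DTSQ models leave out baseline DTSQs, and the responder rule for the two perceived-frequency items gives no direction although a higher score is worse

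*SAP*

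**What the plan says.** **Models.** SAP 2.4.7 compares DTSQs and DTSQc scores at 6 and 12 months by ANCOVA, with a reference to the approach for the continuous efficacy variables. It then gives the terms: "The ANCOVA model with satisfaction score as the dependent variable includes HbA1c target and other stratification factors used at randomization", namely SU use and GLP-1 RA use, plus continuous baseline HbA1c. The GES model in the same section is introduced almost identically: "The logistic model includes HbA1c target and other stratification factors used at randomization".

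For DTSQc, SAP 2.1.7.2 says: "To control for baseline scores, DTSQs will be used as a measure of treatment satisfaction at baseline". Protocol 9.3.1 says the same. Protocol 11.4.4 states an aim of baseline adjustment but stops at similar terms: "To adjust for the baseline differences between treatment groups, logistic regression will be conducted, adjusting for randomization strata of HbA1c target", then SU use, GLP-1 RA use and baseline HbA1c.

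**Responder rule.** SAP 2.1.7.1 uses one form of words for three scores. For total satisfaction: "Percentage of patient responders on total treatment satisfaction score, defined as patients presenting a change from baseline to respectively Month 6 and Month 12", by at least the distribution-based MCID. For perceived hypoglycemia: "presenting a change from baseline to respectively Month 6 and Month 12 of at least the standard MCID". Perceived hyperglycemia is handled in the same way. SAP 2.5.1 sets the standard MCID at half the baseline SD, which is a positive number.

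Total satisfaction runs from 0 to 36, with higher better. Items 2 and 3 run from 0 (the problem is never felt) to 6 (it is felt most of the time). Yet the section describes all three scores as built "such that a higher score would be indicative of better satisfaction".

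**The concern.** A patient's own baseline score is usually the strongest predictor of the follow-up score. Leaving it out widens the interval and lets a chance baseline difference between arms pass into the estimate. For DTSQc it also leaves a control that both documents announce without any model that applies it.

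The responder rule is the more serious of the two. A change of at least a positive number, taken with its sign, is an increase. That is an improvement on total satisfaction and a deterioration on items 2 and 3. Taken as an absolute change, the rule pools patients who improved with patients who worsened. Nowhere does the SAP say that a decrease is the response, and its one general statement on direction points the wrong way for these items. Perceived hypoglycemia is the patient-reported counterpart of the trial's main claim, so a responder table with the arms in reverse order would mislead on a point that readers will look at.

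**Working it through.** The plan gives no figure to reproduce here, and the documents give no DTSQ correlations or item SDs. The correlations, SDs and mean changes below are assumptions, shown over a range.

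**1. Is baseline DTSQs in any DTSQ model?**

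- SAP 2.4.7, DTSQs and DTSQc: HbA1c target, SU use, GLP-1 RA use, baseline HbA1c.
- SAP 2.4.4.2, the efficacy ANCOVA referred to: the same terms plus baseline BMI.
- SAP 2.4.7, GES logistic model: the same four terms as the DTSQ model. GES has no baseline measurement, so the list is complete for GES.

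No printed list contains DTSQs. The list given for DTSQ is the one that suits an outcome without a baseline.

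**2. Cost of the omission.** In SD units, with n per arm and correlation ρ between baseline and follow-up:

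- SE of the difference = √(2/n): 0.0347 at n = 1662 (full sample) and 0.0392 at n = 1300 (half of 2600, the low end of the SAP's stop-recruitment estimate).
- 95% half-width: 1.96·SE unadjusted, 1.96·SE·√(1−ρ²) adjusted.
- Variance cut = ρ². Equivalently, the unadjusted variance is larger by 1/(1−ρ²) − 1.
- Chance imbalance carried into the unadjusted estimate, 95% range = ±ρ·1.96·SE.

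| | ρ | variance cut | half-width, n = 1662 | half-width, n = 1300 | carried imbalance, 1662 / 1300 |
|---|---|---|---|---|---|
| DTSQs | 0.3 | 9% | 0.068 → 0.065 | 0.077 → 0.073 | ±0.020 / ±0.023 |
| DTSQs | 0.6 | 36% | 0.068 → 0.054 | 0.077 → 0.062 | ±0.041 / ±0.046 |
| DTSQc | 0.1 | 1% | 0.068 → 0.068 | – | ±0.007 / – |
| DTSQc | 0.3 | 9% | 0.068 → 0.065 | – | ±0.020 / – |

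The unadjusted excess is 1/0.91 − 1 = 10% at ρ = 0.3 and 1/0.64 − 1 = 56% at ρ = 0.6. For DTSQc, ρ is the assumed size of its correlation with baseline DTSQs.

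If the DTSQs outcome is instead an unadjusted change from baseline, its variance relative to the adjusted model is 2(1−ρ)/(1−ρ²) = 2/(1+ρ). That is 54% higher at ρ = 0.3 and 25% higher at ρ = 0.6.

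**3. Direction of the responder rule, by hand.** Take the baseline SD as 1, a threshold of 0.5 and ρ = 0.5. The SD of change is then √(2(1−0.5)) = 1. Let the mean change on item 2 or 3 be −0.3 in the better arm and −0.1 in the other.

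- Increase of at least 0.5: 1 − Φ(0.8) = 21.2% against 1 − Φ(0.6) = 27.4%. The worse arm leads.
- Decrease of at least 0.5: Φ(−0.2) = 42.1% against Φ(−0.4) = 34.5%. The better arm leads.
- Absolute change of at least 0.5: 63.3% against 61.9%. Almost no contrast.

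**4. The same on a 0–6 item.** Correlated normal scores were rounded and truncated to 0–6, with at least 1,000,000 simulated patients per arm. The true arm difference was 0.5 points, the SD 1.2, 1.6 or 2.0, ρ 0.3 or 0.6, and the baseline mean 1.0, 1.5, 3, 3.5 or 4, which makes 30 scenarios. Half the observed baseline SD was 0.52 to 0.90, so any one-point move counts as a change.

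| start | decrease rule | signed-change rule | absolute rule |
|---|---|---|---|
| low (1.0 or 1.5; better arm unchanged, other arm up 0.5) | better arm ahead by 6–13 points | worse arm ahead by 9–18 | worse arm ahead by about 2–6 |
| high (3 to 4; arms end at 2.5 and 3.0) | better arm ahead by 8–17 | worse arm ahead by 5–14 | better arm ahead by 0–9 |

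One low-start case (mean 1.0, SD 1.2, ρ 0.6), better arm first: decrease rule 28% against 17%; signed-change rule 28% against 46%. The signed-change rule reversed the arms in all 30 scenarios.

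**The case against.** **The list may not be closed.** The SAP says the model includes these terms, not that it has no others. It refers to an approach in which HbA1c is adjusted for its own baseline, and SAP 2.1.7.2 could be read as supplying the missing DTSQc term. That reading is possible. But the sentence after the reference lists the terms and names baseline HbA1c where baseline DTSQs would stand. A programmer working from 2.4.7 would leave it out.

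**Change scores already use the baseline.** SAP 2.5.1 bases effect sizes on LS mean changes from the MMRM or ANCOVA, and 2.1.7.1 lists change from baseline as an evaluated quantity. This is fair, and the raw-score figures do not describe that analysis. But an unadjusted change model also loses precision (25 to 54% above), and the same covariate cures it. With that covariate, the score model and the change model give the same treatment difference.

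**Protocol 11.4.4 is weak evidence.** Its list is attached to a logistic regression in a paragraph that also covers the hypoglycemia questionnaire, while the scores are assigned to an MMRM. This is accepted. The point rests on SAP 2.4.7 set against 2.1.7.2 and protocol 9.3.1.

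**A baseline rule exists.** SAP 2.1.1 defines the efficacy baseline as the last value up to the date of randomization. It does not name the questionnaires, and it would admit a Day 1 score. Protocol 10.1.1.2 lists the randomization call ahead of the questionnaire. That list may not be a sequence, but nothing ensures that the Day 1 score comes before the patient knows the arm in this open-label trial.

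**Nobody would count worsening as response.** The item anchors are clear, no between-arm test of responders is planned, and the SAP promises a check: "Cumulative distribution function of score changes from baseline at 6 and 12-months will be plotted by treatment arm for each of the 3 DTSQs" scores. The plot would show the true direction. The harm is therefore a responder table that disagrees with its own plot.

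**Conclusion.** Both parts hold, and both should be corrected.

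The covariate point is a contradiction for DTSQc and an incomplete specification for DTSQs. It does not bias the comparison, and every half-width and carried imbalance in the working lies well below the 0.2 SD that the SAP itself calls negligible. Correcting it tightens intervals and is not expected to change a conclusion. For DTSQc, the only direct contradiction, the gain is small.

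The responder rule is wrong as written for items 2 and 3 under the signed reading and uninformative under the absolute one. Total satisfaction has no stated sign either, but there the signed reading gives the right answer. That the rule can reverse the arms follows from the item scales alone. The size of the reversal depends on the assumed means, SDs, correlations and 0.5-point difference.

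All these endpoints are exploratory with no multiplicity control (SAP 2.4.4.3), and the primary result is untouched.

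**What to change.** In SAP 2.4.7, add the matching baseline DTSQs score as a covariate in every DTSQs and DTSQc model: total satisfaction for total satisfaction, item 2 for item 2, item 3 for item 3.

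State which pre-treatment value is the baseline, since DTSQs is collected at both Screening and Day 1. The Screening value certainly precedes randomization. Use that same value for the change scores and for the SD behind the MCID thresholds.

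In SAP 2.1.7.1, define response on items 2 and 3 as a decrease of at least the standard MCID and on total satisfaction as an increase of at least its own MCID. Limit the sentence on higher scores to total treatment satisfaction.

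The cost is SAP wording and one covariate that is already collected, with no change at the sites. Patients without a baseline DTSQs need a simple stated rule so that they are not dropped, for example the mean baseline score over both arms combined.

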2.4.8 Analyses of Health economic endpoints

Detailed analysis methods for health resource utilization will be described in a separate analysis plan.

2.5 DATA HANDLING CONVENTIONS

2.5.1 General conventions

Reference day

The reference day for the calculation of extent of exposure, time to onset and relative days is the day of the first IMP administration, denoted as Day 1.

Demographic formulas

Age (years) will be calculated as follows = Integer ($[(\text{Date of informed consent} - \text{Date of birth} + 1)/365.25]$)

BMI (kg/m²) will be calculated as follows = $(\text{Weight in kg})/(\text{Height in meters}^2)$

In case of partial dates, ([Section 2.5.3](#)).

Disease history

Diabetes duration of (years) will be calculated as follows = $(\text{Date of informed consent} - \text{Date of diagnosis of diabetes} + 1)/365.25$.

Age at diagnosis of diabetes (years) will be calculated as follows = $(\text{Date [MM-YYYY]} \text{ of diagnosis of diabetes} - \text{date [MM-YYYY]} \text{ of birth} + 1)/365.25$.

In case of unavailable date of birth, only the year of the date of diabetes diagnosis and the year of the date of birth (retrieve using the age recorded at screening) will be considered in the age at diagnosis of diabetes calculation.

Duration of previous non-insulin anti-hyperglycemic treatment (years) will be calculated as follows = $(\text{Date of informed consent} - \text{date of first dose of previous non-insulin anti-hyperglycemic treatment} + 1)/365.25$

IMP exposure

IIMP (U/Kg) will be determined as:

IMP dose (U)/Body weight (kg) obtained at a given visit.

Laboratory efficacy data conversion

HbA1c conversion:

IFCC in mmol/mol = $(10.93 \times \text{NGSP in \%}) - 23.5$.

FPG and SMPG conversion:

From mg/dL to mmol/L: $\times 0.0555$,

From mmol/L to mg/dL: $\times 18.0148$.

Renal function formulas

Conversion for serum creatinine:

From mg/dL to $\mu\text{mol/L}$: x 88.402.

Conversion for total bilirubin:

From mg/dL to $\mu\text{mol/L}$: x 17.104.

Creatinine clearance value will be derived using the equation of Cockcroft and Gault, using weight assessed at the same visit:

For Male:

$$\text{CL}_{\text{Cr}} (\text{mL/min}) = \frac{[(140 - \text{age}(\text{years})) \times \text{weight}(\text{kg})]}{[0.814 \times \text{serum creatinine}(\mu\text{mol/L})]}$$

For Female: result above multiplied by 0.85.

Hepatic function formulas

Conversion for total bilirubin:

From mg/dL to $\mu\text{mol/L}$: 17.10.

Patient reported outcomes

Minimal clinically important difference:

- Standard MCID threshold will be calculated as half- SD at baseline.
- Distribution-based MCID threshold will be calculated as $SD_{\text{baseline}} \times \sqrt{1-r}$ where r is the Cronbach's α reliability coefficient at baseline.

Effect sizes (ES)

- Within and between effect sizes (ES) interpretation is the following:
 - An $ES < 0.2$ is considered negligible,
 - $0.2 \leq ES < 0.5$ is considered small,
 - $0.5 \leq ES < 0.8$ is considered moderate,
 - $ES \geq 0.8$ is considered important.
- Within ES, calculated at treatment arm level, indicates if a change from baseline to the Month 6/Month 12 is clinically meaningful:

$$\frac{\text{LS mean change from baseline at timepoint } t}{\text{Pooled baseline SD}}$$

- Between ES, calculated when comparing treatment arm, indicates if the mean changes from baseline to Month 6/Month 12 are clinically meaningful between treatment arm,
$$\frac{\text{Difference in LS means between groups at timepoint } t}{\text{Pooled baseline SD}}$$
- Both LS means will be determined using the MMRM/ANCOVA whereas pooled baseline SD will be determine from descriptive statistic at baseline.

$$\frac{N_{\text{Toujeo}} \times SD_{\text{Toujeo}} + N_{\text{standard_of_care_basal_insulin}} \times SD_{\text{standard_of_care_basal_insulin}}}{N_{\text{Toujeo}} + N_{\text{standard_of_care_basal_insulin}}}$$

Table 5 - Unexpected Scoring

Scoring issues	DTSQs	DTSQc
In between score	If patients answer in between choices, score should be coded as mean of both scores (ie, if between 2 and 3 coded 2.5)	
Item answered twice using 2 consecutive scores	Midpoint score should be used (ie, if 1 and 2 are answered should be coded 1.5)	
Item answered twice but using non-consecutive scores	Score is set to missing	
Item is circled but accompanied by word	Only score should be taken into account	
If respondent as circle word of the extremes of the scale instead of value	Score should be the nearest value (ie, 0 or 6)	Score should be the nearest value (ie, -3 or 3)

ABBREVIATION: DTSQs = diabetes treatment satisfaction questionnaire status version.

Table 6 - PRO missing data handling

PRO scales	Score	Number of items included in score derivation	Minimum number of items required for score calculation
DTSQs	Total treatment satisfaction score	6	4
	Perceived frequency of hyperglycemia score	1	1
	Perceived frequency of hypoglycemia score	1	1
DTSQc	Total treatment satisfaction score	6	4
	Perceived frequency of hyperglycemia score	1	1
	Perceived frequency of hypoglycemia score	1	1

ABBREVIATION: DTSQs = diabetes treatment satisfaction questionnaire status version; DTSQc = diabetes treatment satisfaction questionnaire change version.

DTSQc and DTSQs total treatment satisfaction score

If no more than 2 out of the 6 questions comprising the treatment satisfaction score are missing, the treatment satisfaction score is imputed by calculating the average of the scores from the answered questions, dividing this sum by the number of answered questions and multiplying the average by six.

2.5.2 Data handling conventions for secondary efficacy variables

Fasting condition

FPG measurement not collecting in fasting condition will not be used in the analyses.

Invalid laboratory data

HbA1c or FPG measurements flagged as invalid by the laboratory will not be used in the analyses.

Treatment persistence/switch

A switch is defined by:

- A switch from Toujeo IMP to any commercial “standard of care” basal insulin or,
- A switch from “Lantus or Levemir” IMP basal insulin to commercial Toujeo.

Change in “standard of care” basal insulin to another basal insulin not being considered as a “switch”.

Remain on assigned therapy is defined by,

- Neither permanently withdraw,
- Nor switch:
 - From IMP Toujeo to Lantus or Levemir insulin,
 - Or from “standard of care” basal insulin to commercial Toujeo,
- Assigned therapy refers to the treatment allocated by IRT: Toujeo or Lantus/Levemir,
- Commercial Toujeo not being allowed in both treatment arms.

Persistence is defined by,

- Remained on assigned therapy.

HbA1c target and severe and or symptomatic hypoglycemia

HbA1c target missing data handling,

- Patients with missing HbA1c data at respectively Month 6 and Month 12 will be regarded as not having reached the HbA1c target (ie, as failure) at each given time-point.

Symptomatic hypoglycemia target missing data handling

In case of at least one symptomatic event with glycemic value missing it will be considered that the patients experiences at least:

- One document symptomatic hypoglycemia (BG ≤ 70 mg/dL [≤ 3.9 mmol/L]) and,
- One document symptomatic hypoglycemia (BG < 54 mg/dL [< 3.0 mmol/L]).

In case of at least one symptomatic event with timing missing it will be considered that the patients experiences at least:

- One symptomatic hypoglycemia event occurring at any time of the day and,
- One nocturnal symptomatic hypoglycemia event.

Composite endpoints missing data handling

- For each cases presented above regarding missing HbA1c values the patient will be considered as failure for each composite endpoint of the corresponding randomized period.
- For each case presented above regarding missing hypoglycemia event information the patient will be regarded as failure for each related composite endpoint.
- In case of premature end of study during the 6 month randomized period the patient will be considered as failure for each composite endpoint relative to the 6-month and the 12 month period.
- In case of premature end of study during the 12 month randomized period the patient will be considered as failure for each composite endpoint relative to the 12-month period.

Change in HbA1c category

Patients with missing:

- Baseline HbA1c will be regarded as not having reached the HbA1c target at Month 6 and Month 12.
- HbA1c data at respectively Month 6 and Month 12 will be regarded as not having reached the HbA1c target at each given time-point.

